2.3.1 Baseline characteristics

Baseline characteristics of subjects are defined as baseline values of the last available and eligible observation at or before randomization covering all subjects, including:

- Continuous:
 - Age (years)
 - Birth weight (kg)
 - Body Mass Index
 - Serum taurine concentration (relative concentration standardized by quality-control samples)
- Categorical:
 - Sex (1,Boy;2,Girl)
 - Nationality (1,Han; 2,Other)
 - Residential area (1,Urban;2, Rural)
 - Household monthly income (1,<=8500;2,>8500 and <20000;3,>=20000 and <50000; 4,>=50000)
 - Number of siblings (0,Single child; 1,One; 2,Two or more)

- Nourish style (0,Parental; 1,Grandparental; 2,Mixed)
- Paternal occupation (1,Civil servant;2 Farmer;3,Techican;4, Freelancer)
- Maternal occupation (1,Civil servant;2 Farmer;3,Techican;4, Freelancer)
- Allergy history (0,No; 1, Yes)
- Birth defects (0,No; 1, Yes)
- Abnormal birth history (0,No; 1, Yes)
- Serious medical history (0,No; 1, Yes)
- Receiving intervention previously (0,No; 1, Yes)
- Baseline physical examination (0,Normal; 1,Abnormal)
- ASD severity (0, Normal;1,Marginal;2,Mild;3,Medium;4,Severe;5,Extremely severe)

Baseline characteristics of subjects will be presented as mean and standard deviation for continuous variables with normal or approximately normal distribution; otherwise, median values and interquartile range (IQR) will instead be calculated. Categorical variables will be described as proportions(number of subjects within category \div all subjects $\times 100\%$).

2.3.2 Primary endpoints

The primary endpoints are defined as change in scores of ASD-related scales from baseline at M0 to M3.

Descriptive statistics of primary endpoints

Mean and standard deviation of primary endpoints at each visit, and changes of mean and standard deviation from baseline to each visit will be presented.

Primary analysis for primary endpoints

Using unimputed data of primary endpoints in FAS, exploratory mixed-effects models, preferably generalized linear mixed model (GLMM) for repeated measures analysis, in the condition for endpoints of >2 visits. This analysis investigates if there are group-specific differences over time. The maximum likelihood method will be used to estimate the mean difference between the two groups and their 95% CI, with Gaussian distribution and identity link function; baseline score, group (group), time point (visit) and group \times visit interaction as fixed effects. The time point(visit) is treated as categorical variable in the models. Random slope with unstructured covariance will be preferred as priority; if convergence is not able to be achieved, random intercept will be performed as an alternative.

Otherwise, ANCOVA will be performed to estimate the mean difference between the two groups and their 95% CI, with group (group) as independent variable, and baseline score, time point (visit) and group \times visit interaction as covariates for outcomes with only 2 visits available. The available visits are defined as >10 observations at a single visit. The reason for this alternative method is explained in the Change Log.

For imputed data of primary endpoints, multiple imputation will be considered for handling missing outcomes. More details are described in 2.3.4.

Secondary analysis for primary endpoints

● Per-protocol analysis

Using unimputed data of primary endpoints in PPAS, exploratory mixed-effects models, preferably generalized linear mixed model (GLMM) for repeated measures analysis, in the condition for endpoints of >2 visits. Otherwise, ANCOVA will be performed if only 2 visits are available for the scores of ASD-related scales. The statistical method is the same as primary analysis for primary endpoints.

● Covariate-adjusted analysis

Covariate-adjusted analysis for primary endpoints is performed in FAS and PPAS using the same statistical method as primary analysis.

Covariates are baseline values (missing imputed) including:

- Age (years)
- Sex (1,Boy;2,Girl)
- Serum taurine concentration (relative concentration standardized by quality-control samples)

- The following covariates will be adjusted only if imbalanced baseline characteristics between group, and further filtered to avoid strong correlation or collinearity in case of linear violation.
- Birth weight (kg)
- Body Mass Index
- Nationality (1,Han; 2,Other)
- Residential area (1,Urban;2, Rural)
- Household monthly income (1,<=8500;2,>8500 and <20000;3,>=20000 and <50000; 4,>=50000)
- Number of siblings (0,Single child; 1,One; 2,Two or more)
- Nourish style (0,Parental; 1,Grandparental; 2,Mixed)
- Paternal occupation (1,Civil servant;2 Farmer;3,Techican;4, Freelancer)
- Maternal occupation (1,Civil servant;2 Farmer;3,Techican;4, Freelancer)
- Allergy history (0,No; 1, Yes)
- Birth defects (0,No; 1, Yes)
- Abnormal birth history (0,No; 1, Yes)
- Serious medical history (0,No; 1, Yes)
- Receiving intervention previously (0,No; 1, Yes)
- Baseline physical examination (0,Normal; 1,Abnormal)

Analysis based on imputation missing baseline covariates data

- Continuous: If no assessments are available, the mean of baseline values within the same sex and age(± 1 year) is used as the baseline value.
- Categorical: If no assessments are available, a new category coded as 999 is used as the baseline value.

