2.1 Sample size determination

Sample size calculation is precluded from this trial due to exploratory design, as well as a lack of literature and data. 60 subjects (30 per group) are expected to meet the regular outpatient workload in the study site, which will be expected to reach the size within a year.

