2.3 Statistical analysis

Effect endpoints will be analyzed using the FAS and PPAS; safety endpoints will be analyzed using the SAS.

Results from effect endpoints will generally be accompanied by two-sided 95% confidence intervals(CI) and corresponding p-values. Significant difference will be claimed if two-sided 95% CI lie away from null. Effect size will be evaluated by corresponding Cohen's D values, which are calculated as mean difference between groups divided by standard deviation for each endpoint in corresponding analysis set (details in appendix Table 1).

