2.3.6 Statistical software

STATA® (version 15.1, Stata Corp, Texas, USA) will perform all data analyses and generate most data displays. R4.1.2 (Vienna, Austria) may also be used for some data analyses and generating statistical graphs.

3. Change log

Version	Date	Reasons for change
0.0	18 Aug 2023	Clinical Trial registration
1.0	7 Mar 2024	Clinical assessments at M1 and M2 were cancelled because clinicians found it difficult for subjects to keep intense clinical visits;
2.0	10 Jan 2025	Secondary endpoints updated
2.5	17 Feb 2025	Supportive endpoint analysis and Other sensitivity analysis updated.
3.0	28 Feb 2025	As drop-outs in M6,M9,M12 for Gesell, CARS and WISC are more than expected (<10 at each visit), ANCOVA will be preferred as an alternative.

4. Appendix

Table 1 The formulas for calculating Cohen's D values

Condition	Statistical display	Formula
-----------	---------------------	---------

Population estimated mean group difference in change over time	$\beta_{T-T0} (95\%CI)$	$\frac{\beta_{T-T0}}{(upperlimit - lowerlimit) \times \frac{2 \times 1.96}{\sqrt{N_{T-T0}}}}$
--	-------------------------	---

Abbreviations: A:placebo group; B, taurine group; T, time visit; T0,baseline.

Table 2 The formulas for calculating ASRS T-score

Condition	Age range	Raw score of items	Formula ¹
SC	2-5 years	$\Sigma (i1 i3 i4 i5 i7 i13 i14 i15 i16 i17 i18 i19 i21 i22 i24 i25 i28 i29 i30 i32 i33 i35 i36 i37 i38 i40 i43 i44 i49 i50 i51 i52 i54 i55 i57 i61 i62 i63 i67)$	$50+10 \times ((\text{raw score} - 50.06)/10.12)$
	6-18 years	$\Sigma (i3 i4 i8 i9 i12 i23 i28 i31 i32 i33 i39 i42 i43 i45 i55 i56 i61 i69 i7)$	$50+10 \times ((\text{raw score} - 24.3)/11.95)$
UB	2-5 years	$\Sigma (i2 i8 i9 i10 i11 i12 i20 i26 i27 i39 i41 i42 i45 i46 i47 i48 i53 i56 i60 i64 i65 i69 i70)$	$50+10 \times ((\text{raw score} - 50)/10.51)$
	6-18 years	$\Sigma (i2 i13 i17 i20 i21 i22 i24 i25 i26 i27 i29 i38 i40 i46 i48 i49 i50 i51 i54 i62 i63 i65 i67 i68)$	$50+10 \times ((\text{raw score} - 27.74)/10.79)$
Total	2-5 years	-	$50+10 * ((T \text{ score}_{SC+UB} - 50.03)/10.35)$
	6-18 years	-	$50+10 * ((T \text{ score}_{SC+UB} - 47.89)/7.85)$

¹the reference values for calculation are based on Chinese reference population^{3,4}.

Abbreviations: SC, Social/Communication; UB, Unusual Behaviors

5. References

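### Mixed models fitted by maximum likelihood in about 60 children, with no small-sample degrees of freedom, give 95% confidence intervals about 4–5% too narrow, so the claim rule runs at roughly 6–6.5% instead of 5%

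*SAP*

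**What the plan says.** SAP section 2.3.2 uses a Gaussian mixed model with identity link for endpoints with more than two visits. On estimation it says: "The maximum likelihood method will be used to estimate the mean difference between the two groups and their 95% CI". The mean model has "baseline score, group (group), time point (visit) and group \times visit interaction as fixed effects". On random effects: "Random slope with unstructured covariance will be preferred as priority; if convergence is not able to be achieved, random intercept will be performed". The per-protocol, covariate-adjusted and secondary-endpoint analyses inherit the same method (sections 2.3.2 and 2.3.3.1).

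The interval is the decision rule. Section 2.3: "Significant difference will be claimed if two-sided 95% CI lie away from null".

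On size, section 2.1 says "60 subjects (30 per group) are expected to meet the regular outpatient workload in the study site". A visit counts as available with more than 10 observations (section 2.3.2), so 11 is the smallest a mixed model can keep. Gesell, CARS and WISC move to ANCOVA because of sparse late visits (section 3, version 3.0).

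Section 2.3.2 does not say how the limits are formed. The only hint is Appendix Table 1, "The formulas for calculating Cohen's D values", which converts the width of the model interval with a factor 2 × 1.96.

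**The concern.** Maximum likelihood estimates variances without allowing for the fixed effects fitted, so it biases them downward. Normal limits then ignore the uncertainty in the estimated variances. Both effects shorten the interval, and both matter in a trial of 60 children or fewer.

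Because significance is read directly from the interval, a short interval is a raised false-positive rate. The error always goes the same way, and it recurs in each mixed-model comparison across several scales and visits.

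**Working it through.** **Inputs from the SAP.** Two-sided 5% claim rule (2.3); 60 children, 30 per group (2.1); maximum likelihood, baseline + group + visit + group × visit, random slope preferred and random intercept as fallback (2.3.2); smallest available visit 11 observations (2.3.2).

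**Inputs not in the SAP.** The critical value is taken as 1.96, inferred from Table 1. Variance components and visit counts for the scales that stay in the mixed model are assumptions. The SAP gives no SD, effect size or power: "Sample size calculation is precluded from this trial due to exploratory design, as well as a lack of literature and data". The nominal 5% error is therefore the only figure to test.

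**Step 1. The nominal figure.** 2 × P(Z > 1.96) = 5.0%. This reproduces the rule, but only as a large-sample value.

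**Step 2. Closed form for a single visit with p mean parameters.** Error under maximum likelihood with 1.96 limits = 2 × P(t with n−p df > 1.96 × √((n−p)/n)). For baseline-adjusted groups, p = 3.

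- n = 60: 1.96 × √(57/60) = 1.910 on 57 df, giving 6.1%.
- n = 40: 1.96 × √(37/40) = 1.885 on 37 df, giving 6.7%.
- Width ratio at n = 60: (2.0025/1.96) × √(60/57) = 1.048, so a corrected interval is about 5% wider.
- If t limits were used but maximum likelihood kept, n = 60: 2.0025 × √(57/60) = 1.952 on 57 df, giving 5.6%.

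This is a guide to the mechanism only. The SAP's mixed model has several visits and pools variance across them.

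**Step 3. Simulation of the SAP's model under the null.** 3,000 trials per scenario; Monte Carlo SE = √(0.05 × 0.95/3000), about 0.4 points. Both methods were run on the same data.

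| Scenario | Children per visit | ML with 1.96 | REML with Satterthwaite t | Corrected/ML width |
|---|---|---|---|---|
| Random slope, M1–M3 | 60, 60, 60 | 6.5, 6.5, 5.9% | 5.6, 5.5, 4.8% | 1.04 |
| Random slope, six visits | 60, 58, 55, 40, 25, 12 | 5.8, 5.4, 4.9, 5.8, 5.8, 6.9% | 4.8, 4.8, 4.1, 4.9, 5.0, 4.9% | 1.04 rising to 1.06 |
| Random slope, M3/M6/M9/M12 | 50, 25, 15, 11 | 6.4, 6.8, 7.7, 7.4% | 4.9, 5.0, 5.3, 4.7% | 1.06 rising to 1.13 |
| Random intercept, correct, six visits | 60 down to 12 | 5.0–6.3% | 4.6–5.6% | 1.03–1.04, flat |
| Random intercept fitted, slopes truly vary | 60 down to 12 | up to 9.5% | up to 8.1% | 1.03–1.04 |

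The gap between methods on the same data is about 1 point at M3 with 60 complete children (5.9 − 4.8). It is about 2.5 points at the visits with 15 and 11 children (7.7 − 5.3 and 7.4 − 4.7). In the six-visit slope panel, the visit with 55 children showed 4.9% before correction and 4.1% after, so single cells should not be over-read.

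A separate simulation (8,000 trials per cell, random intercept, within-child correlation 0.5 and 0.8) gave 5.5–5.9% at 30 per arm and 5.6–6.4% at 20 per arm for the last-visit contrast.

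**Step 4. Covariate-adjusted models.** Age, sex and serum taurine are always added, so p = 6 in the single-visit form: 1.96 × √(54/60) = 1.859 on 54 df, giving 6.8% at n = 60 and, by the same formula, 8.0% at n = 40. If imbalanced covariates brought p to 10 (an assumption), the n = 60 figure would be 8.0%. These are again guides to direction.

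**The case against.** The strongest reply is that the effect is small where it matters most. At M3 with 60 children the excess is about one point, the trial is labelled exploratory, and no powered confirmatory test depends on it. That stands, and it sets the severity.

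Second, normal limits are not stated. The evidence is one constant in an effect-size formula. As it reads in the available text, that formula multiplies the interval width by 2 × 1.96/√N, which would not recover a standard deviation; this may be an artefact of text extraction. The inference remains reasonable because no degrees-of-freedom rule appears anywhere, but it is an inference. Maximum-likelihood bias would remain under t limits (5.6% in the single-visit form).

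Third, a reader might infer much larger errors at sparse visits. The single-visit formula gives 13.3% at n = 11 (p = 3), and a simulated random-intercept trial with six children per arm gives 8.7–10.1%. Neither describes this plan: the mixed model applies only with more than two visits, and section 2.3.3.1 fits all time points of a scale together, so a sparse visit borrows variance from fuller ones.

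Fourth, a reader might infer that every scale and visit is affected, and sparse visits always most. Visits with 10 or fewer observations are not available, and Gesell, CARS and WISC go to ANCOVA, for which the SAP names neither maximum likelihood nor normal limits. Under a correct random intercept the narrowing is flat at 3–4%; it grows at sparse visits only under the random slope.

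**Conclusion.** The point holds at modest size. As written, the mixed-model intervals are about 4–5% too narrow at n = 60, and the claim rule runs at about 6–6.5% at M1–M3 with complete data. Under the preferred random slope it runs at about 7–8% at retained visits with 11–15 children, and somewhat higher in covariate-adjusted models.

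This rests on 1.96 limits (inferred from Table 1) and on assumed variance components and visit counts. It covers only endpoints with more than two available visits.

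A reader might also attribute the error of a misspecified random-intercept fallback to maximum likelihood. The check does not support that: of 9.5% at n = 12, 8.1% remains after correction, so most of that excess comes from the covariance structure.

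Severity: minor to moderate.

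**What to change.** In section 2.3.2, replace maximum likelihood by REML with Kenward-Roger or Satterthwaite degrees of freedom (name one) and t-based 95% limits. State that this applies to all mixed models: FAS, PPAS, covariate-adjusted and secondary endpoints. In Appendix Table 1, use the model standard error directly, or the t quantile that matches the interval, instead of 1.96, and check the printed formula at the same time.

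The cost is a line of wording and a software setting, with no new data. Intervals become about 4–5% wider at n = 60. In the assumed random-slope panels they become about 6% wider at a visit with 12 of 60 children, and 9–13% wider at visits with 15 and 11 children in a panel that starts at 50. In the correctly specified models simulated, error returned to 4.1–5.6%. The change does not repair a random-intercept fallback that misses real variation in slopes.

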2.3.3 Secondary and supportive endpoints

2.3.3.1 Secondary endpoints

Descriptive statistics of secondary endpoints

Mean and standard deviation of secondary endpoints at each visit, and changes of mean and standard deviation from baseline to each visit will be presented.

Analysis for Secondary endpoints of the same scale in M6,M9 and M12:

Using unimputed data of secondary endpoints with the same exploratory mixed-effects models as primary endpoints (i.e. the same scale in different time points will be included simultaneously), preferably generalized linear mixed model (GLMM) for repeated measures analysis. The statistical method is the same as primary analysis, per-protocol analysis and covariate-adjusted analysis for primary endpoints.

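### The random slope has no named time variable, and the random-intercept fallback miscalibrates the visit-specific confidence intervals unless variances given baseline are equal across visits

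*SAP*

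**What the plan says.** For endpoints with more than two available visits, SAP section 2.3.2 plans a Gaussian mixed model: "preferably generalized linear mixed model (GLMM) for repeated measures analysis, in the condition for endpoints of >2 visits". The fixed effects are baseline score, group, visit and group by visit. On estimation: "The maximum likelihood method will be used to estimate the mean difference between the two groups and their 95% CI". On time: "The time point(visit) is treated as categorical variable in the models". The random part follows directly: "Random slope with unstructured covariance will be preferred as priority; if convergence is not able to be achieved, random intercept will be performed". No numeric time variable, visit-specific residual variance, residual correlation structure or robust standard error is mentioned.

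Section 2.3.3.1 carries the model to M6, M9 and M12: "Using unimputed data of secondary endpoints with the same exploratory mixed-effects models as primary endpoints", with the clarification that "the same scale in different time points will be included simultaneously". Section 2.3 sets the claim rule: "Significant difference will be claimed if two-sided 95% CI lie away from null". Appendix Table 1 also uses the confidence limits to compute Cohen's D.

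Two Change log entries limit the scope. Version 1.0 cancels clinical assessments at M1 and M2, although section 1.1.3 still lists those visits for seven scales. Version 3.0 moves Gesell, CARS and WISC to ANCOVA because fewer than 10 observations were available at each of M6, M9 and M12.

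**The concern.** Two things are badly fixed.

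First, the preferred model is ambiguous. Because the slope sentence follows the one declaring visit categorical, it can be read as a random effect for each visit. With one score per child per visit, that model cannot separate the residual variance from the visit effects. Two analysts could fit different models, and a convergence message, possibly differing by scale, would decide which covariance model is reported.

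Second, the fallback is restrictive. A random intercept gives every visit the same variance and every pair of visits the same correlation. Since baseline score is a covariate, the variance that matters is the variance given baseline. If a score at 12 months is less well predicted by baseline than a score at 3 months, that variance grows with time even when the raw standard deviations are equal. The pooled variance is then too large for early visits and too small for late ones. At stake are the error rate of the claim rule and the width of intervals that feed Cohen's D.

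**Working it through.** The SAP has no calculated figure to reproduce here; its 60 children (30 per group, section 2.1) are a feasibility number.

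**Step 1, identifiability.** With K response visits there are K(K+1)/2 variances and covariances to estimate. A random effect for categorical visit with unstructured covariance plus a residual variance has K(K+1)/2 + 1 parameters.

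| Response visits | Parameters | Rank of the map to variances and covariances |
|---|---|---|
| 3 (M1, M2, M3) | 7 | 6 |
| 4 (M3, M6, M9, M12) | 11 | 10 |
| 6 (M1 to M12) | 22 | 21 |

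The excess is always one. Only the split between residual and visit effects is lost. The total covariance, and so the group difference and its interval, remains identified if the software returns a fit. With a slope on numeric month there are 4 parameters (two variances, one covariance, one residual) and rank 4 for every set of three or more visits tested.

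**Step 2, random-intercept intervals.** Assumptions, none of them in the SAP: equal raw standard deviations, complete data, and correlation with baseline at t months of r × exp(−t/λ), with r from 0.7 to 1.0 and λ from 18 to 36 months. This implies correlations of 0.59-0.92 at M3 and 0.36-0.72 at M12.

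- Variance given baseline at month t, in units of the raw variance: v(t) = 1 − r² × exp(−2t/λ).
- Standard-error ratio, reported over true: √(mean of v over the visits in the model / v(t)).
- Two-sided error: 2 × (1 − Φ(1.96 × ratio)).

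Example with r = 0.9, λ = 18 and visits M1, M2, M3, M6, M9, M12: v is 0.275, 0.351, 0.420, 0.584, 0.702 and 0.787, with mean 0.520. At M3 the ratio is √(0.520/0.420) = 1.11, error 2.9%. At M12 it is √(0.520/0.787) = 0.81, error 11.1%.

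Over the whole assumed range:

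| Visits in the model | M3 ratio | M3 error | M12 ratio | M12 error |
|---|---|---|---|---|
| M1 to M12 | 1.04-1.27 | 1.3-4.2% | 0.71-0.92 | 7.2-16.3% |
| M3, M6, M9, M12 | 1.07-1.46 | 0.4-3.6% | 0.82-0.95 | 6.3-10.7% |
| M1, M2, M3 only | 0.82-0.98 | 5.5-10.6% | – | – |

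The second row applies if the M1 and M2 cancellation covers these scales. The third applies if the primary visits are modelled separately from follow-up.

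**Step 3, checks by simulation** (30 per arm, maximum likelihood, 1.96 multiplier).

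- Decaying correlation, r 0.9-1.0, 4,000 trials per setting. Random intercept on M1 to M12: error 1.6-3.4% at M3 and 11.8-17.2% at M12. Random intercept on M1 to M3: 8.0-11.7% at M3. With visit-specific variances and baseline by visit: 5.3-6.6% at every visit.
- Exchangeable correlation of 0.5, visits M3 to M12, complete data, 400 runs (Monte Carlo error about 1 point). The two columns on the right give coverage of the 95% interval.

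| SD given baseline, M3 to M12 | Model | M3 | M12 |
|---|---|---|---|
| equal | random intercept | 95.5% | 93.8% |
| 0.8 to 1.2 | random intercept | 98.8% | 89.2% |
| 0.8 to 1.2 | slope on numeric month | 96.3% | 93.2% |
| 0.8 to 1.2 | unstructured | 94.3% | 93.5% |

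The remaining shortfall of 1-2 points under the unstructured model is what maximum likelihood with 1.96 would be expected to give at this sample size.

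**The case against.** A reader might infer that the planned model cannot be identified, that the M3 and M12 intervals are therefore wrong, and that false claims at the primary time point are inflated. The document does not support that.

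- Categorical visit as a fixed effect with a random slope on numeric month is an ordinary, identified model, and the wording allows it. If it converges, the fallback never applies. Even on the categorical reading, a returned fit gives an identified group contrast. Failure to converge is a risk, not something the SAP states.
- Rising variance is an assumption. With equal variances given baseline and exchangeable correlation, the random-intercept intervals are correct apart from small-sample error. If variance falls over time, the errors reverse.
- The size depends on how well baseline predicts later scores. At r = 0.7, M12 error in the six-visit model is only 7.2-7.7%.
- In the joint model described in section 2.3.3.1, the M3 interval is too wide under decaying correlation, so the cost there is precision. Inflation at M3 needs a separate M1 to M3 fit, which the M1 and M2 cancellation may rule out for these scales.
- The trial is labelled exploratory, and an unstructured covariance for six visits needs 21 parameters from 60 children.

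All of this stands as a limit on the claim. It does not remove the missing slope variable, or a fallback whose calibration rests on an unstated equal-variance condition while section 2.3 still uses the interval to declare significance.

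**Conclusion.** The point holds in a conditional form and should be addressed. The slope variable is unnamed; read as categorical visit, the preferred model is over-parameterised by exactly one, and non-convergence alone selects the random intercept. That fallback gives correct visit-specific intervals only if variances given baseline are equal across visits.

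If they rise in the way assumed, the main exposure is at M12: roughly 6-16% error instead of 5%, depending on r, λ and whether M1 and M2 are in the model. At M3 the error is below 5% in either joint model and above it only in a separate M1 to M3 fit. These figures rest on assumed correlations, equal raw standard deviations and complete data.

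The point covers ATEC, ASRS, SRS, IMFeD, 6-GSI, CSHQ and PSI, not the three scales moved to ANCOVA. Because the trial is exploratory, this is a calibration fault to correct rather than one that invalidates the analysis.

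**What to change.** Replace the random-effects sentence in section 2.3.2 with a repeated-measures model on the post-baseline scores: no random effects, unstructured residual covariance across visits within child, and fixed effects baseline, group, visit, group by visit and baseline by visit. In Stata this is `mixed` with `residuals(unstructured, t(visit))`. Preferably fit it by REML with a small-sample degrees-of-freedom correction such as Kenward–Roger.

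State a fallback order that keeps visit-specific variances: heterogeneous Toeplitz, then heterogeneous AR(1). Section 2.3.6 already allows R if these are easier to fit there. If a random-effects model is kept, name numeric month as the slope variable and use cluster-robust standard errors. State also which visits enter each scale's model, given the M1 and M2 cancellation.

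The cost is a few lines of SAP text and a changed model call. The downside is more covariance parameters (6 for three visits, 10 for four, 21 for six) and possible non-convergence when late visits are sparse, which the fallback order is there to handle.

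### Fifteen covariates enter the adjusted analyses only if imbalanced between randomised arms and are then filtered for collinearity, with no cut-off for either step, so the adjusted model is not fixed in advance

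*SAP*

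**What the plan says.** SAP section 2.3.2 lists a covariate-adjusted analysis among the secondary analyses of the primary endpoints: "Covariate-adjusted analysis for primary endpoints is performed in FAS and PPAS using the same statistical method as primary analysis". It therefore inherits the primary model, which has "baseline score, group (group), time point (visit) and group \times visit interaction as fixed effects".

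Three covariates are added unconditionally: age, sex and "Serum taurine concentration (relative concentration standardized by quality-control samples". A second list is conditional: "The following covariates will be adjusted only if imbalanced baseline characteristics between group". What passes that step is "further filtered to avoid strong correlation or collinearity in case of linear violation". The conditional list runs from birth weight to "Baseline physical examination (0,Normal; 1,Abnormal" and has 15 entries. For a missing categorical covariate, "If no assessments are available, a new category coded as 999 is used as the baseline value".

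Section 2.3.1 says how baseline characteristics are summarised but gives no rule for comparing the arms. It also lists "ASD severity (0, Normal;1,Marginal;2,Mild;3,Medium;4,Severe;5,Extremely severe", a variable that is in neither covariate list of section 2.3.2.

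The rule reaches further than this one analysis. Section 2.3.3.1 applies the covariate-adjusted method to the secondary endpoints, and section 2.3.4 builds the therapy-adjusted analysis on it.

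**The concern.** There are two faults.

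First, the rule cannot be carried out reproducibly. Imbalance could be judged by a p-value, a standardised difference or by eye, at any cut-off. The collinearity filter has no threshold and no order of removal. The SAP does not say whether imbalance is judged once or separately in the FAS and the PPAS. Nor does it say that the set is settled before outcomes are seen; the documentation before database lock that section 2.2 requires concerns excluded observations, not covariates. Two competent analysts could follow the text and fit different models.

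Second, imbalance is a poor basis for selection even with a cut-off. Under randomisation, differences between arms in these variables arise by chance. A trigger based on them can add variables unrelated to outcome and leave out conditional candidates that predict outcome but happen to balance.

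At stake are the adjusted estimates, confidence intervals and p-values for the ten scales in section 1.1.3. Section 2.3 claims a significant difference whenever a 95% interval excludes the null, so these analyses can produce claims. They cannot serve as a fixed robustness check if their covariates are open.

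**Working it through.** The SAP gives no figure to reproduce, so the check is how far the unstated cut-off moves the model.

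**Inputs from the SAP**
- Conditional covariates (2.3.2): 15, of which 2 are continuous and 13 categorical.
- Planned size (2.1): 60 subjects, 30 per group.

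**Assumptions**
- The cut-offs below are illustrative, because the SAP states none.
- Arms are balanced in expectation on these variables.
- The standardised mean difference (SMD) is treated as approximately normal with standard error √(2/30) = 0.258. For the categorical variables this is a rough approximation.

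**Expected number flagged by chance, before the collinearity filter**

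For a test at level a, the expected number is 15 × a. For an SMD cut-off c, P(|SMD| > c) = 2 × [1 − Φ(c / 0.258)], and the expected number is 15 times that.

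| Cut-off | Chance per covariate | Expected number of 15 |
|---|---|---|
| p<0.05 | 0.05 | 0.75 |
| p<0.10 | 0.10 | 1.5 |
| p<0.20 | 0.20 | 3.0 |
| SMD>0.50 | 0.053 | 0.8 |
| SMD>0.25 | 0.333 | 5.0 |
| SMD>0.20 | 0.439 | 6.6 |
| SMD>0.10 | 0.699 | 10.5 |

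These expected counts do not require the covariates to be independent.

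**Chance that at least one is flagged**

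This does assume independence: 1 − (1 − a)^15.
- p<0.05: 1 − 0.95^15 = 53.7%
- p<0.10: 1 − 0.90^15 = 79.4%
- p<0.20: 1 − 0.80^15 = 96.5%

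Positive correlation, which is plausible among income, residence and the two parental occupations, would lower these percentages.

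**Upper bound on model size**

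If all 15 entered, the terms would be: 2 continuous + 8 binary + income 3 + siblings 2 + nourish style 2 + two occupations at 3 each = 23. With age, sex and taurine that is 23 + 3 = 26, against at most 60 children. A missing-value level on each of the 13 categorical candidates would raise 23 to 36.

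This bound is remote. Under independence, all 15 are flagged with probability 0.05^15 (negligible) at p<0.05, and 0.699^15 ≈ 0.5% even at SMD>0.10, before any filtering.

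**The case against.** The best defence is about scope. The trial is labelled exploratory, this is a secondary analysis, and the primary FAS model contains none of the 15 candidates. The most obvious prognostic terms (baseline score, age, sex, serum taurine) enter whatever their balance. The trigger looks at baseline values, not outcomes. Imbalance is also the same for all ten scales within an analysis set, so that step does not invite a choice scale by scale. Stating a metric and cut-offs would remove the ambiguity without deleting the rule.

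Most of this stands and limits the point. It does not answer it. A stated cut-off would make the rule reproducible, but the rule would still select on chance differences.

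Three stronger readings are tempting, and the SAP does not support them.

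- **That leaving out ASD severity makes the adjusted effect data-driven.** The omission is fixed in advance; only the imbalance and collinearity steps are open. Baseline score is always in the model, so for CARS, ATEC, ASRS and SRS severity is largely covered. The omission has some force for Gesell, WISC, IMFeD, 6-GSI, CSHQ and PSI.
- **That the model will carry 26 parameters for 60 children.** That is an extreme upper bound, as shown above. Over-fitting is a risk under loose cut-offs, not an established result.
- **That the primary result is compromised.** The conditional list does not touch it.

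**Conclusion.** The point holds for the covariate-adjusted analyses of the primary and secondary endpoints and for the therapy-adjusted analysis. Neither the imbalance trigger nor the collinearity filter is defined, their timing relative to outcomes is not stated, and chance imbalance is the wrong criterion in a randomised comparison.

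The size is best given as the spread in expected additions: from 0.75 to about 10.5 of 15 covariates across the cut-offs considered. This rests on 30 children per arm, on the assumed cut-offs and on the normal approximation. It is counted before the collinearity filter, whose effect cannot be calculated because it is undefined.

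This should be changed, but it does not threaten the primary analysis.

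**What to change.** In section 2.3.2, delete the conditional-entry rule and the collinearity filter. State that the covariate-adjusted model for every scale, in both the FAS and the PPAS, contains baseline score, age, sex and serum taurine in addition to group, visit and their interaction. The secondary-endpoint and therapy-adjusted analyses then inherit the same set. Report the other 15 characteristics by arm descriptively only.

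ASD severity is an optional addition, mainly for the scales whose baseline score does not measure autism symptoms (Gesell, WISC, IMFeD, 6-GSI, CSHQ, PSI). Add it only if this is specified before outcomes by arm are seen, and say how its six levels are coded. If outcomes by arm have already been seen, keep to the set already fixed and label any wider adjustment post hoc.

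The cost is a change of SAP wording, with no new data. The downside is that a chance imbalance in an unlisted variable would be described, not adjusted for.
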